## **7.4. Early Termination of Trial**

The trial may be stopped early for any one or more of the following reasons:

- If the monitoring of the clinical trial reveals unacceptable levels of adverse events, even though some of the participants may not be affected;
- If the Investigator does not adhere to the protocol or decides to stop the study for any reason, with appropriate notification.

In the event of early termination of the trial, the HREC will be notified.

# **8. NUMBERING**

Participant numbering will occur sequentially commencing with '01'.

## 9. EQUIPMENT TO BE USED / STANDARD & NON-STANDARD PRACTICE PROCEDURES

### 9.1. Standard Equipment and Procedures:

- **Visual Acuity:** Measurement of the standard of vision achieved with spectacles using standard letter charts. Measurements are taken under monocular and/or binocular conditions.
- **Slit-Lamp Biomicroscopy:** A specialised microscope with its own light source is used to examine the anterior eye.
- **Subjective questionnaire:** The “ocular surface disease index” questionnaire will be administered. This consists of 12 questions relating to the participant’s dry eye symptoms.
- **Lipid layer thickness:** The LipiView® Ocular Surface Interferometer (TearScience®) measures the absolute thickness of the tear film lipid layer by analyzing more than one billion data points of the interferometric image of the tear film. The patient’s eye is positioned in front of an illumination source that is directed toward the tear film on the corneal surface. Light from this source passes through the tear film and is specularly reflected into a camera. The camera records a 20-second video of the tear film interference and subsequently displays a value in interferometric colour units (ICUs) where 1 ICU approximates 1 nm of lipid layer thickness.
- **Tear Break-Up Time:** Following instillation of fluorescein, tear break up time will be measured.
- **Fluorescein Assessment:** The ocular surface is assessed by instilling a harmless fluorescent dye called ‘fluorescein’ directly to the inferior bulbar conjunctiva using a sterile strip impregnated with fluorescein and moistened with sterile saline. The eye is assessed with the slit-lamp biomicroscope using a cobalt blue filtered light and a Wratten 12 filter.

### 9.2. Non-Standard Equipment and Procedures:

Non-standard procedures that may be performed include:

- **Tear evaporation rate:** The Vapometer is a closed chamber device which is used for measuring transepidermal water loss. Participants will be seated upright on a chair and provided with a distance fixation target. To minimize the effect of skin evaporation, petroleum jelly (Vaseline, <http://www.unilever.com.au/brands-in-action/detail/Vaseline/299339/>) will be applied over the upper eyelid and the surrounding areas. The VapoMeter will then be placed over the eye and a non-invasive measurement of tear evaporation will be taken within 10 seconds. Participants will be instructed not to blink during open eye measurement and to maintain a normal straight gaze at the fixation target. Evaporation rates with the eyes closed will also be taken, in order to account for the skin evaporation from eyelids and surrounding skin tissue.

### 9.3. Maintenance and Calibration of Equipment

Equipment will be monitored regularly for maintenance and calibration as per relevant company and product manuals.

## 10. TREATMENT OF PARTICIPANTS

### 10.1. Administration of drops

The Investigator will provide instructions to the study participants as to the drop instillation technique but will not be cognizant to the randomisation schedule and will not be present during the dispensing of the drops to maintain masking.

### 10.2. Drop Storage and Accountability

#### 10.2.1. Storage Requirements

Drops will be stored at room temperature in a secure storeroom/cupboard. The storage facility should be kept locked to prevent unauthorized access and to ensure accountability of the study lenses at all times.

#### 10.2.2. Accountability

An Eye Drop Tracking spreadsheet is used for keeping track of who, where and when drops have been issued or dispensed to.

- **Receipt of drops:** Once invoice has been checked, the drops will be entered into the Eye Drop Tracking spreadsheet.
- **Issue of Drops to Clinical Trial Participants:** The Optometrist is responsible for documenting the dispensing of the drops on the Eye Drop Tracking spreadsheet.
- **Disposal of Unused Supplies:** Instruction will be obtained from the Sponsor as to how to handle returned, unused drops.

### 10.3. Concomitant Therapy

Whilst participating in this clinical trial participants are not permitted to enrol in other clinical trials.

Participants must not use or have a need for any systemic or topical medications which may alter normal ocular findings/are known to affect a participant's ocular health/physiology either in an adverse manner or risk providing a false positive.

Participants will be instructed to refrain from wearing contact lenses for 1 week prior to the study and for the duration of the study.

### 10.4. Participant Instructions

#### General instructions to all participants

Contact the clinic immediately if problems are experienced or if they have any questions or concerns.

## 11. ASSESSMENT OF EFFICACY

### 11.1. Parameters

A measurable difference in subjective symptoms and/or objective tear lipid layer thickness or tear breakup time between Optimel Manuka eye drops and Systane Ultra Eye drops after 4 weeks of daily use.

### 11.2. Methods

Subjective symptoms will be measured using the OSDI questionnaire.

Tear film inferior lipid layer thickness (LLT; nm) will be measured using the LipiView II (Johnson and Johnson Vision, USA). The participant's eye is positioned in front of an illumination source that is directed toward the tear film on the corneal surface. The camera records a 20-second video of the tear film interference and subsequently displays a value in interferometric colour units (ICU), where 1 ICU approximates 1nm of lipid layer thickness.

Fluorescein tear break-up time (TBUT; sec) (Opti-Strip-FL, Optimed, Lane Cove West, NSW, Australia) was measured viewed with a yellow Wratten filter (No. 12, Kodak) and cobalt light of the slit lamp biomicroscope. Three consecutive TBUT measurements for each eye were taken by a single masked investigator.

## 12. ASSESSMENT OF SAFETY

### 12.1. Parameters

- Visual acuity
- History
- Ocular health
- Corneal staining

### 12.2. Methods

Visual acuity will be measured using standard letter charts. The study participant's habitual visual acuity will be assessed.

History (including medical and general health) will be recorded at the study visit.

Slit lamp biomicroscopy will be assessed to evaluate ocular surface health.

An optometrist will be available for the duration of the study. Participants will be advised to contact the Optometrist immediately of any event not normal e.g. unusual redness, pain, irritation, etc. At the clinic, the Optometrist will briefly assess the eye on a slit-lamp under low illumination to ascertain the nature of the condition, if any. If an adverse event occurs, the appropriate procedures will be conducted, including referral for medical treatment if necessary. Any adverse events will be followed until complete resolution to the reasonable satisfaction of the participant and the investigator.

### 12.3. Definitions

#### 12.3.1. Adverse Events

**Adverse Event:** Any undesirable clinical occurrence in a participant, that includes a clinical sign, symptom or condition and/or observation of an unintended technical performance or performance outcome.

Adverse Events may be classified as Serious, Significant, Non-significant or Unanticipated as defined further on.

#### 12.3.2. Serious Adverse Events

Any adverse medical occurrence that:

- led to death.
- led to a serious deterioration in health of a Participant user or other. This would include:
  - a life threatening illness or injury.

- a permanent impairment of body function or permanent damage to a body structure.
  - a condition requiring hospitalisation or increased length of existing hospitalisation.
  - a condition requiring unnecessary medical or surgical intervention.
  - foetal distress, foetal death or a congenital abnormality/birth defect.
- might have led to death or a serious deterioration in health had suitable action or intervention not taken place.

Specifically for the eye, Serious Adverse Events include but are not limited to:

- permanent decrease in best-corrected visual acuity ( $\geq 2$  lines)
- central corneal opacities
- central corneal neovascularisation – in the central 4mm of the cornea
- central corneal opacities – in the central 4mm of the cornea
- infectious corneal ulcers
- uveitis
- iritis
- endophthalmitis
- hypopyon
- hyphema
- penetration of bowman's membrane
- persistent epithelial defect
- limbal cell damage leading to conjunctivalisation.

Serious adverse events are reportable.

### 12.3.3. Significant Adverse Events

Significant Adverse Events are those that are symptomatic (excluding serious adverse events noted above). They include, but are not limited to:

- **Infiltrative keratitis:** Inflammatory reaction of the cornea characterised by anterior stromal infiltrates with or without epithelial involvement. Symptoms include mild to moderate irritation, and redness. Staining may be slight to moderate.
- **Conjunctivitis:** Inflammatory reaction of the conjunctiva characterised by discharge, grittiness, redness and swelling.
- **Corneal Erosion:** Full thickness epithelial loss over a discrete area.

### 12.3.4. Non-Significant Adverse Events

Non-significant Adverse Events are those that treatment, if needed, is usually with over the counter products. They include, but are not limited to:

- asymptomatic infiltrative keratitis
- blepharitis
- meibomitis
- contact dermatitis
- localised allergic reactions.

### 12.3.5. Unanticipated Adverse Events

Adverse events or serious adverse events are considered “unexpected” or “unanticipated” if they do not appear listed in the technical manuals to date. These events require expedited reporting.

### 12.3.6. Event Severity

Events should be rated by a study investigator according to their severity:

- Mild:** No treatment required  
**Moderate:** Treatment required.  
**Severe:** Requires referral to and treatment by an ophthalmologist.

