#### 4.2.1. Risks and Benefits

##### Risks of the Clinical Trial

Although unlikely, it is possible that participants may be allergic to any of the ingredients in the study eye drops. Signs of ocular allergy include swelling, redness, itching and watering of the eyes. Subjects with a known allergy to the study eye drops will not be enrolled. Subjects who experience an allergic reaction will be treated by thoroughly rinsing the eye with preservative free unit-dose saline, continuous monitoring until ocular signs and symptoms have returned to normal, and immediate discontinuation from the study. Subjects may also be referred to the Sydney Eye Hospital for treatment, if required.

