### 12.4.2. Foreseeable Adverse Events

Risks associated with the use of the study eye drops include:

- Eye discomfort/stinging (<30%)
- Eye redness (<10%)
- Blurry vision (<10%)

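### Section 12.3.6 grades event severity by the treatment an event needs and who gives it, so the grades in the safety record need not reflect intensity

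*Combined protocol and SAP*

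**What the plan says.** Section 12.3.6 states its purpose plainly: "Events should be rated by a study investigator according to their severity". It then gives one criterion per grade:

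- **Mild:** "No treatment required"
- **Moderate:** "treatment required"
- **Severe:** "Requires referral to and treatment by an ophthalmologist"

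The events to be graded are defined broadly. Section 12.3.1 opens with "Any undesirable clinical occurrence in a participant" and sets no restriction to the eye. Section 12.3.2 gives general criteria for a serious adverse event, among them death, hospitalisation and "a life threatening illness or injury". A separate list of eye-specific examples follows.

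Section 12.4.2 lists eye discomfort or stinging (below 30%), redness (below 10%) and blurred vision (below 10%) as foreseeable risks of the study drops.

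Section 12.4 expects the sponsor to keep tabulations or line listings of all adverse events. It does not say which columns these contain.

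**The concern.** A severity grade should tell the reader how bad an event was. These criteria record something else: whether treatment was needed and, for the top grade, whether one named specialty had to provide it. The two can diverge in both directions. An intense event may need no treatment, and a grave event outside the eye will normally be treated by other doctors.

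At stake is what the safety record can convey about tolerability. Stinging, redness and blur are the only drop risks for which the protocol gives rates. Where they need no treatment, a slight and an intense occurrence receive the same grade. A later statement that all events were mild could then be true under the definitions and still misinform. If intensity is not recorded when the event occurs, it cannot be reliably reconstructed afterwards.

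**Working it through.** No arithmetic applies, and the plan gives no figure to reproduce. The check reads the definitions literally, applies them to two events, and then looks for any other severity scale and any use of the grade.

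**1. What the criteria measure.** The split between Mild and Moderate depends on whether treatment is required. The split between Moderate and Severe depends on referral to, and treatment by, an ophthalmologist. No grade mentions intensity or functional effect. The grades also overlap as written, because any event that meets the Severe criterion also meets the Moderate one.

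**2. A life-threatening non-ocular event treated by doctors other than an ophthalmologist.**
- It is an adverse event under 12.3.1 and a serious one under 12.3.2.
- It fails the only criterion for Severe.
- Treatment is required, so it is Moderate.
- The cap follows from the treating specialty and holds at any intensity.

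**3. Stinging that requires no treatment.**
- It is foreseeable under 12.4.2.
- It meets the Mild criterion whatever its intensity.
- The test is whether treatment is required, not whether it was given. Stinging that needed treatment but went without it would be Moderate.

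**4. Is there another scale?** None appears in the text available. Section 4.2.4 uses mild to severe for dry eye disease. Section 12.3.3 uses mild, slight and moderate to describe the irritation and staining of infiltrative keratitis. Neither is a scale for grading events. Section 12.6 (Referrals) is listed in the table of contents but was not in the text available, so it could not be checked.

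**5. Where is the grade used?**

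| Decision or output | What it depends on | Uses the 12.3.6 grade? |
|---|---|---|
| Ethics committee reporting (12.4) | Seriousness | No |
| Regulator reporting (12.4.1) | Serious and unanticipated | No |
| Discontinuation and follow-up (12.5) | Any adverse response | No |
| Early termination (7.4) | Unacceptable levels of adverse events | Not mentioned |
| Analysis (13.1.3) | Tear parameters, symptoms, other parameters | Not mentioned |
| Tabulations or line listings (12.4) | All adverse events | Not mentioned, but a natural place for it |

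The defect therefore reaches the recorded grade and any listing or summary that carries it, and no further in the visible text.

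**The case against.** The strongest reply is that the grade decides nothing. Reporting depends on seriousness and expectedness, and discontinuation follows any adverse response. The safety parameters in 12.1 are acuity, history, ocular health and staining. This is correct and sets the limit on the point.

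A second reply is that tolerability can be seen elsewhere. Reasons for discontinuation are to be reported (13.1.3), and symptoms are collected at both visits (section 6). That stands in part: a participant who leaves because of stinging should be visible. Neither source grades the intensity of an individual adverse event.

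Several stronger readings are tempting, but the documents do not support them:

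- **That serious events would be missed or under-reported.** They are captured under 12.3.2 and reported on that basis.
- **That a planned comparison of tolerability between the drops would be misleading.** No comparison by severity grade is planned. That severity will appear in the listings is an inference.
- **That any serious event with a low grade is an error.** Severity and seriousness are separate axes, so a mismatch alone proves nothing. A permanent loss of acuity graded Mild is such a case, and it also assumes that no treatment would be required.
- **That a trivial allergic itch must be Moderate**, because section 4.2.1 says "Subjects who experience an allergic reaction will be treated by thoroughly rinsing the eye with preservative free unit-dose saline". Section 12.3.4 classes localised allergic reactions as non-significant, with treatment only where needed, so this ranking is not forced.
- **That the rates in 12.4.2 give the number of misgraded events, or show that the honey drop stings more.** They are upper bounds on occurrence, given for the study drops together. The documents do not say what share of such events is intense.

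**Conclusion.** The point holds in a limited form. Section 12.3.6 announces a severity rating and supplies a scale of treatment need and provider. On a literal reading, a life-threatening non-ocular event not treated by an ophthalmologist cannot exceed Moderate, and stinging that needs no treatment cannot exceed Mild.

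The harm is confined to the severity grades in the safety record and to any listing or summary built on them. No reporting, withdrawal, stopping or planned efficacy rule is affected. The number of misgraded events cannot be estimated from the documents.

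The conclusion rests on two assumptions: that investigators apply the definitions as written, and that the unavailable section 12.6 contains no other severity scale. The change is worth making because it is nearly free and the lost information is hard to recover, not because the trial's main conclusions depend on it.

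**What to change.** Reword 12.3.6 so that Mild, Moderate and Severe are defined by intensity or by interference with usual activities, with the same definitions for ocular and non-ocular events and no overlap between grades. Do not use interference with drop use, or discontinuation, as a criterion. Section 12.5 discontinues participants who have an adverse response, so such a criterion could push most events into the top grade and lose the distinction again.

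State that severity is graded independently of seriousness under 12.3.2. Record treatment given and referral (including to whom) as separate fields on the case report form, so that what the present scale captures is kept. This changes measurement only and leaves every treatment, referral, withdrawal and reporting rule as it is.

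The cost is one reworded section and one or two more fields on a paper form, with no extra visits or participants. The downside is that grading intensity is slightly more subjective than recording whether treatment was required.

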## 12.4. Reporting

In the event of persistent irritation, redness, reduced visual acuity or any other unusual signs or symptoms, the participants will be advised to contact the investigators immediately.

Non-serious and anticipated adverse events should be recorded as part of Good Clinical Practice. Sponsors are expected to maintain up-to-date tabulations and/or line listings of all adverse events.

All Serious Adverse Events should be reported to the HREC as per their reporting requirements. This should be followed by a more detailed written report commenting on potential confounding factors, results of investigations, treatment required and outcome.

### 12.4.1. Expedited Reporting

UNSW, via the Principal Investigator (PI) of the clinical trial is required to report to the Therapeutic Goods Administration (TGA) single cases of serious and unanticipated adverse events.

- **Fatal or life-threatening unexpected adverse events** – the TGA should be notified as soon as possible but no later than 7 calendar days after first knowledge by the PI that the case qualifies, followed by a complete report as possible within eight additional calendar days.
- **All other serious, unexpected adverse events** – TGA notification as soon as possible but no later than 15 calendar days after first knowledge by the PI that the case meets the minimum criteria for expedited reporting.

In the case of an unexpected and serious adverse event that occurs outside Australia with use of the same product, the TGA and HREC should also be notified. The time frame for this reporting should be within 72 hours of any significant safety issue which has arisen from an analysis of overseas reports or action which has been taken by another country's regulatory agency. This advice must include the basis for such action. Investigators should also be notified, who must in turn notify the HREC.

Reports should be on the 'Medical Incident Report Form' located on the TGA website ([http://www.tga.gov.au/docs/html/forms/iris\\_mdir.htm](http://www.tga.gov.au/docs/html/forms/iris_mdir.htm)) or similar format, and clearly marked 'Clinical Trial Adverse Event' and sent to:

[REDACTED]

### 12.4.2. Foreseeable Adverse Events

Risks associated with the use of the study eye drops include:

- Eye discomfort/stinging (<30%)
- Eye redness (<10%)
- Blurry vision (<10%)

### 12.4.3. Other Observations

There may be other situations that may necessitate rapid communication to regulatory authorities. Scientific and medical judgment should be applied for each situation. In general, information that

might materially influence the benefit-risk assessment of a product or that would be sufficient to consider changes in product administration or in the overall conduct of a clinical investigation represent such situations.

### 12.5. Follow-up

Participants who experience an adverse response will be discontinued from the study and followed up until the condition resolves or the participant is referred to another practitioner.

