## 6. TRIAL DESIGN

This will be a prospective, randomized, single centre, double-masked, randomized dispensing study. There will be 2 visits in total:

- (i) **Baseline (Week 0):** Screening, randomization, informed consent, habitual visual acuity, OSDI, symptom survey, biomicroscopy, tear film assessment and dispensing eye drops.
- (ii) **28 days of treatment  $\pm$  4 days (Week 4):** habitual visual acuity, OSDI, symptom survey, biomicroscopy, tear film assessment and study exit.

Standard ocular examination and non-standard ocular examination procedures will be carried out at the scheduled visits.

*Standard optometric procedures at each visit include:*

- Habitual visual acuity
- Slit lamp evaluation including corneal details
- Subjective questionnaire: Ocular Surface Disease Index (OSDI)
- Tear breakup time
- Tear lipid layer thickness

*Non-standard optometric procedures may include:*

- Tear evaporation rate

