## **7.2. Participant Withdrawal**

Participants may be permanently discontinued from the clinical trial for any of the following reasons:

- If, in the Investigator's opinion, it is in the best interest of the participant;
- Persistent clinical trial-related symptoms/complaints that are not correctable;
- Has a serious adverse event/serious adverse event that is eye related and/or which, in the Investigator's opinion, requires withdrawal of the participant;
- Participant voluntarily withdraws consent from the clinical trial (i.e. Revocation of Consent);
- If a participant is not compliant with the clinical trial requirements and instructions;
- Protocol violations/deviations.

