## **7.3. Withdrawal and Follow-up Procedure**

This study comprises four visits for each participant. Any participants who wish to be withdrawn from the study will be exited upon request.

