#### 13.1.3. Analysis

Participants who complete the study treatment will be included in the analysis dataset. Reasons and frequency distribution of participants discontinued will be reported.

Data will be summarised as means  $\pm$  standard deviations for variables measured on an interval scale and median  $\pm$  inter-quartile range for ordinal variables. Statistical tests will be employed to determine significant differences in tear parameters, subjective symptoms and other parameters between Optime! Manuka+ Eye Drops and Systane Ultra eye drops. Normality will be assessed using the Shapiro-Wilk test. Independent t-tests will be used for comparison of continuous normally distributed data between the test and control groups. Non-parametric data will be analysed using Mann-Whitney U test. Proportions will be compared using  $\chi^2$  tests and associations will be examined using Pearson's correlation. The level of significance is set at  $\alpha=0.05$ . Statistical analysis will be performed using SPSS software V.22.0. The difference between the 28 days and baseline data will be used to quantify the treatment effect.

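### Section 12.5 makes study exit mandatory for an undefined adverse response, at odds with 7.2; anyone exited before day 28 has no efficacy outcome and is dropped by the completers-only analysis

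*Combined protocol and SAP*

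**What the plan says.** Section 12.5 sets a mandatory rule: "Participants who experience an adverse response will be discontinued from the study and followed up until the condition resolves", or until referral to another practitioner. The trigger, an adverse response, occurs nowhere else in the document. Section 12.3 defines adverse events and their classes and 12.3.6 grades severity, but 12.5 uses none of these terms.

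Section 7.2 is discretionary: "Participants may be permanently discontinued from the clinical trial for any of the following reasons". The grounds listed there include the participant's best interest in the investigator's opinion, "Persistent clinical trial-related symptoms/complaints that are not correctable", and a serious event that is eye related and/or judged to require withdrawal. Section 4.2.1 has its own rule that an allergic reaction leads to immediate exit from the study.

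On visits, Section 6 states: "There will be 2 visits in total". Table 4 agrees (baseline and day 28); 7.3 mentions four visits, but nothing else in the protocol supports that. For those who leave, 7.3 says only: "Any participants who wish to be withdrawn from the study will be exited upon request".

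On analysis, 13.1.3 states: "Participants who complete the study treatment will be included in the analysis dataset". The outcome is a change score: "The difference between the 28 days and baseline data will be used to quantify the treatment effect". It adds: "Reasons and frequency distribution of participants discontinued will be reported".

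**The concern.** Two rules cover the same participant. One compels exit and the other leaves it to judgement, and nothing says which governs. Clinicians could handle identical complaints differently.

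The consequence reaches the efficacy analysis. Exit is from the study and not only from the drops. Follow-up under 12.5 concerns the condition, with no tear-film or OSDI assessment at day 28. The completers-only rule then removes the participant after randomisation for a reason related to how the drop was tolerated. Discomfort is also close to what the symptom endpoint measures, so those removed may differ in outcome from those kept. If such losses differ between the arms, in number or in kind, the comparison of lipid layer thickness and symptoms no longer rests on the randomised groups. Reporting the reasons for discontinuation makes the loss visible but does not recover the outcomes.

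**Working it through.** **Step 1: the exit rules compared.**

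| Section | What happens after an adverse event | Exit? |
|---|---|---|
| 12.5 | Follow-up to resolution or referral | Mandatory; trigger undefined |
| 7.2 | Investigator decides, on listed grounds | Discretionary |
| 4.2.1 | Allergic reaction: rinse, monitor | Mandatory; trigger specific |
| 12.2 | Appropriate procedures, referral if needed, follow-up | Not mentioned |
| 12.4 | Non-serious anticipated events recorded | Not mentioned |

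The nearest defined term, Adverse Event in 12.3.1, is broad enough to include a symptom, and 12.4.2 lists stinging (<30%), redness (<10%) and blurred vision (<10%) as foreseeable adverse events. A literal reading of 12.5 could therefore reach mild stinging.

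**Step 2: the plan's own allowance.** From 4.2.4 and 13.1.1: 38 completers, 20% dropout. 38 / 0.80 = 47.5, rounded up to 48, which reproduces the planned enrolment. The allowance is 48 − 38 = 10 losses, or 10/48 = 20.8%. (Section 6.1.3 asks for 46 completers; that is a separate inconsistency.)

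**Step 3: illustration of loss under the literal reading.** Let s be the stinging rate and r the share of stinging reported before day 28, so the loss probability is p = s × r. Stinging is taken as the only cause of loss and events as independent. The documents give only the ceiling for s, not split by drop, and nothing for r; all values below are assumed.

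| s | r | p | Expected losses of 48 | P(at least 38 complete) |
|---|---|---|---|---|
| 0.29 | 0.25 | 0.0725 | 3.48 | >0.99 |
| 0.29 | 0.50 | 0.145 | 6.96 | 0.92 |
| 0.29 | 0.75 | 0.2175 | 10.44 | 0.52 |
| 0.29 | 1 | 0.29 | 13.92 | 0.14 |
| 0.20 | 0.50 | 0.10 | 4.80 | 0.99 |
| 0.20 | 0.75 | 0.15 | 7.20 | 0.90 |
| 0.20 | 1 | 0.20 | 9.60 | 0.64 |
| 0.10 | 1 | 0.10 | 4.80 | 0.99 |

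The last column is P(X ≥ 38) for X ~ Binomial(48, 1 − p). At s = 0.29, expected losses exceed 10 only if r exceeds 0.2083 / 0.29 = 0.72. Other dropout would lower these probabilities. Under the narrower reading this particular loss is close to nil.

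**Step 4: illustration of bias.** In each arm, let p be the share removed and d the mean day-28 change of those removed minus that of those retained. The mean of everyone randomised to the arm equals the retained mean plus p × d, so analysing completers alone shifts the between-arm difference by |p1·d1 − p2·d2|. Assume stinging in 25% versus 10%, half reported early, and a common d. The shift is (0.125 − 0.05) × d = 0.075d, which is 0.0375 SD for d = 0.5 SD and 0.075 SD for d = 1 SD. It is zero when p1·d1 = p2·d2. The arm split and d are assumed, and the sign is unknown.

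**The case against.** The strongest reply is that 12.5 was never meant to catch mild stinging. Sections 12.2 and 12.4 describe treatment, follow-up and recording with no exit; 12.3.6 has a mild grade needing no treatment; 4.2.1 reserves mandatory exit for allergy. The wording of 12.5 itself, a condition that resolves or is referred, suggests a clinical finding. Burning and irritation are among the entry symptoms. This stands: the narrower reading is the more likely intent, although 12.5 does not state it. Section 12.6, listed in the contents as Referrals, was not available to check.

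A reader might infer that up to 30% of participants must leave. The documents do not support that. The figure is a ceiling, and there is no visit between baseline and day 28. Section 10.4 asks participants to contact the clinic about any problem, but 12.2 speaks of abnormal events and 12.4 of persistent ones, so early reporting of brief stinging cannot be assumed. Events first mentioned at day 28 need not cost any data.

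A reader might also say that 7.2 confines symptom-related exit to persistent complaints. It does not, because the best-interest ground is wider. The conflict is between mandatory and discretionary wording.

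Finally, the completers-only rule is a weakness whatever 12.5 says. That is true, but 12.5 and 4.2.1 are stated routes by which adverse reactions feed into it, so the two are best amended together.

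**Conclusion.** The point holds in this form: an undefined mandatory exit rule conflicts with a discretionary one. On the literal and the narrower reading alike, participants exited before day 28 have no planned efficacy measurement and are excluded by 13.1.3. The comparison is biased only if those losses differ by arm in number or in outcome; the documents neither show nor exclude this. Size and direction are unknown.

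The calculations are illustrations. They do not establish that the trial will miss 38 completers, which at a 29% rate would need roughly three quarters of stinging to be reported early, nor that a material bias exists. Because the plan gives no effect size, SD or power behind 38, a shortfall cannot be turned into a documented loss of power. The case for acting is that a stated rule discards outcomes after randomisation for reasons linked to treatment, when the visit that could supply them is already scheduled.

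**What to change.** 1. Amend 12.5 so that discontinuation follows the 7.2 criteria and the 4.2.1 allergy rule. Replace the undefined trigger with a term from 12.3, and state that mild foreseeable events listed in 12.4.2 are recorded and followed without mandatory exit.
2. In 12.5, 7.2 and 4.2.1, separate stopping the drops from leaving the study. Ask participants who stop drops for an adverse event to attend the scheduled day-28 visit if willing and if it is safe, and record whether they are on or off drops. Withdrawal of consent still ends participation.
3. In 13.1.3, make the main analysis all participants with day-28 data in their randomised arm, and keep the completers analysis as supporting.

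The cost is a wording amendment with ethics committee approval; no visit is added. Some day-28 values will be off drops, which can dilute the on-treatment contrast; the supporting completers analysis shows the result without them. Participants who do not attend day 28 remain missing, so reasons for discontinuation should still be reported, by arm.
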